Secondary Objectives:

- To investigate the preliminary anti-tumor activity of BMS-986156 administered alone and in combination with nivolumab in subjects with advanced solid tumors
- To characterize the PK of BMS-986156 administered alone and in combination with nivolumab
- To characterize the immunogenicity of BMS-986156 administered alone and in combination with nivolumab, and the immunogenicity of nivolumab administered with BMS-986156.

Study Design:

This is a Phase 1/2a, open-label study of BMS-986156 administered as a single agent and in combination with nivolumab in subjects with advanced solid tumors.

The study will be conducted in 5 parts. Parts A and B will consist of dose escalation with BMS-986156 administered as a single agent (Part A) or in combination with nivolumab (Part B) in subjects with advanced solid tumors. Starting dose selection of BMS-986156 for Part B was determined using all available safety (clinical and laboratory), PK [REDACTED] data and will be one dose level lower than the already tolerated dose in the ongoing monotherapy dose escalation in Part A (See [Section 1.1.4](#) for details). Subsequently, escalation in the Parts A and B will proceed in parallel.

Nivolumab will be administered as a dose of 240 mg administered Q2W for all combination dose cohorts (Parts B and D).

Nivolumab will be administered as a dose of 480 mg every 4 weeks for combination dose cohorts Part E

Cohort expansions were evaluated with BMS-986156 monotherapy (Part C) and combination therapy (Part D).

Part C consists of cohort expansion with BMS-986156 monotherapy in 2 disease-restricted populations, NSCLC with progressive or recurrent disease (per RECIST v1.1) during or after anti-PD-1 or anti-PD-L1 therapy following prior platinum doublet-based chemotherapy, and persistent, recurrent, or metastatic cervical cancer, of approximately 25 subjects each.

Part D consists of cohort expansion with BMS-986156 administered in combination with nivolumab in disease-restricted populations as follows (i) NSCLC, (ii) cervical, (iii) bladder cancer, (iv) squamous cell carcinoma head and neck, (v) ovarian cancer, and (vi) hepatocellular carcinoma of approximately 40 subjects each.

Part E consists of cohort expansion with BMS 986156 administered in combination with nivolumab in cervical cancer (cohort 9) and other solid tumor types (Cohort 10). Each cohort will contain approximately 40 subjects each.

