Part E will consist of an initial safety lead in period of up to 12 subjects. Six subjects need to complete the 14-day observation period before the full expansion cohorts, of up to 40 subjects, are opened. Patients who discontinue for reasons other than disease progression, death, or treatment-related toxicity may be replaced. An observation period of 14 days has been chosen based on pharmacokinetic (PK) modeling and simulation for BMS-986156, based on PK parameters derived from preclinical studies (Section 1.1.5).

Duration of Study: The total duration of time for any individual subject in both monotherapy and combination arms of the study is expected to be approximately 3.1 years.

Number of Subjects: Approximately 310 subjects will be dosed.

Study Population:

Male and/or female subjects who are at least 18 years old, and satisfy eligibility criteria by medical history, physical examination (PE), 12-lead electrocardiogram (ECG), and clinical laboratory evaluations will be included to participate in the study as follows:

For Dose Escalation in Parts A and B: Subjects with any solid tumor type (with the exception of primary central nervous system tumors) are eligible to enroll. All subjects will be required to document availability of archival tumor tissue before study drug is administered. If archival tumor tissue is not available, subjects must consent to a tumor biopsy.

For Cohort Expansion (Parts C, D, and E): Subjects must have one of the tumor types defined above.

Women of childbearing potential (WOCBP) must not be nursing or pregnant and must be using an acceptable method of contraception for at least 4 weeks before dosing. WOCBP must have a negative pregnancy test within 24 hours prior to dosing with study medication.

Study Drug: Includes Investigational Product (IP) as listed:

Study Drug for BMS-986156 and Nivolumab

Medication	Potency	IP/Non-IP
BMS-986156 Injection	100 mg/vial (10 mg/mL)	IP
nivolumab Injection	100 mg/vial (10 mg/mL)	IP

Study Assessments:

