As a Phase 1 dose-escalation trial, the sample size at each dose in these arms depends on observed toxicity and posterior inference. Approximately 60 subjects are expected to be treated during the dose-escalation phase (around 30 subjects for BMS-986156 monotherapy and around 30 subjects for BMS-986156 in combination with nivolumab). Initially up to 3 subjects will be treated at the starting dose levels of BMS-986156 or BMS-986156 in combination with nivolumab. Additional cohorts of approximately 3 evaluable subjects will be treated in recommended dose levels per BLRM (-Copula) during the dose-escalation phase. At most 12 DLT-evaluable subjects will be treated at each dose level.

Cohort Expansion:

Part E includes two cohorts with one as Cervical and another one as the mixed tumors for signal seeking and exploration of Q4W dosing. Due to the purpose of signal confirming in cervical cancer and heterogeneity of response rates of the mixed tumors cohort, approximately 40 subjects are planned for each cohort in part E. For initial safety evaluation of 480 mg BMS-986156/480 mg nivolumab Q4W in Part E, 6 subjects will be enrolled and followed for a minimum of 2 weeks (please refer to [Section 3.7](#) for the rationale for 2 week period) prior to opening Part E to full enrollment.

The planned sample size for each of the expansion cohorts serve as a guidance. Final decision will be made by the sponsor based on totality of data available by then.

If in a cohort of 40 subjects 10, or 15 responses are observed, then the lower limit of the one-sided 90% exact binomial CI for the ORR is 16%, and 27% respectively. These calculations are made using the Clopper-Pearson method for exact confidence intervals. If the true ORR in a tumor type is 40%, then with 40 subjects in a tumor type, there is 93% chance of observing at least 12 responses, and 87% chance of observing at least 13 responses, and there is 7% chance of observing 11 or fewer responses (false negative rate).

Primary Endpoints:

- The primary objective of the study is to establish MTD/MAD/alternate dose(s). The assessment of safety will be based on the incidence of AEs, serious adverse events (SAEs), adverse events leading to discontinuation, and deaths. In addition clinical laboratory test abnormalities will be examined.

Secondary endpoints:

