3 INVESTIGATIONAL PLAN

3.1 Study Design and Duration

This is a Phase 1/2a, open-label study of BMS-986156 administered as a single agent and in combination with nivolumab in subjects with advanced solid tumors.

The study will be conducted in 5 parts. Parts A and B will consist of dose escalation with BMS-986156 administered as a single agent (Part A) or in combination with nivolumab (Part B) in subjects with advanced solid tumors. Starting dose selection of BMS-986156 for Part B (combination with nivolumab) was determined using all available safety (clinical and laboratory), PK, [REDACTED] and modeling recommendations within Bayesian hierarchical modeling framework by incorporating single agent toxicity profiles of both BMS-986156 (Part A) and nivolumab (data from CA209003 study, a phase 1 nivolumab monotherapy data in advanced solid tumors) and will be one dose level lower than a dose already tested and shown to be tolerated in ongoing monotherapy dose escalation in Part A [REDACTED]. Subsequently, escalation in the 2 parts will proceed in parallel.

A dose -1 cohort of 3 mg has also been included and will only be explored in the event 10 mg dose of BMS-986156 is determined to exceed the MTD in monotherapy or in combination with nivolumab (Table 3.4.1-1).

At no point will the dose of BMS-986156 administered in combination with nivolumab in Part B exceed doses of BMS-986156 that have been demonstrated previously to be safe in the monotherapy dose escalation arm (Part A), nor at any point during Part B escalation will the BMS-986156 dose exceed the highest dose determined to be tolerated in Part A.

Nivolumab will be administered as a dose of 240 mg every 2 weeks for combination dose cohorts (Parts B and D).

Nivolumab will be administered as a dose of 480 mg every 4 weeks for combination dose cohorts Part E

Part C consists of cohort expansion with BMS-986156 monotherapy in 2 disease-restricted populations, NSCLC with progressive or recurrent disease (per RECIST v1.1) during or after anti-PD-1 or anti-PD-L1 therapy following prior platinum doublet-based chemotherapy, and persistent, recurrent, or metastatic cervical cancer, of approximately 40 subjects each.

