8 STATISTICAL CONSIDERATIONS

8.1 Sample Size Determination

8.1.1 Dose Escalation

As a Phase 1 dose-escalation trial, the sample size at each dose in these arms depends on observed toxicity and posterior inference. Approximately 60 subjects are expected to be treated during the dose-escalation phase (around 30 subjects for BMS-986156 monotherapy and around 30 subjects for BMS-986156 in combination with nivolumab). Initially approximately 3 subjects will be treated at the starting dose levels of BMS-986156 or BMS-986156 in combination with nivolumab. Additional subjects will be treated in recommended dose levels per BLRM (-Copula) during the dose-escalation phase. At most 12 DLT-evaluable subjects will be treated at each dose level.

Additional subjects may be treated at any dose level at or below the MTD or MAD (if no MTD is identified) for further evaluation of safety, [REDACTED] PK parameters as required. At most 12 DLT-evaluable subjects will be treated at each dose level.

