8.1.2 Cohort Expansion

Part C contains 2 cohorts of 25 subjects each in monotherapy cohort expansion,. Each cohort in the combination cohort expansion phase (parts D and E) will contain approximately 40 subjects. Forty subjects in parts D and E are planned with the goal of achieving a width of approximately 20% in the 95% confidence interval for ORR, and to provide additional information on safety. Patients in any cohort who discontinue for reasons other than disease progression, death, or treatment-related toxicity may be replaced.

For initial safety evaluation of 480 mg BMS-986156/480 mg nivolumab Q4W in Part E, 6 subjects will be enrolled and followed for a minimum of 2 weeks (please refer to [Section 3.6](#) for the rationale for 2 week period) prior to opening Part E to full enrollment.

If in a cohort of 40 subjects, 10 or 15 responses are observed, then the lower limit of the one-sided 90% CI for the ORR would be 16%, and 27% respectively. These calculations are made using the Clopper-Pearson method for exact confidence intervals. If the true ORR in a tumor type is 40%, then with 40 subjects there is 93% chance of observing at least 12 responses, and 87% chance of observing at least 13 responses, and there is 7% chance of observing 11 or fewer responses.

Continuous interim evaluations and monitoring of safety and efficacy based on the totality of data will be carried out throughout the expansion phase. Decisions regarding continuing enrollment based on these evaluations will be made through discussion between the Sponsor and investigators based on totality of data and overall clinical activity (such as but not limited to duration of response, quality of response, clinical assessment of response and/or SD and safety). The number of subjects receiving treatment of the planned sample size is approximate and may exceed the specified numbers due to unknown time to response and true recruitment rate (i.e additional participants may be enrolled to compensate the 25%-35% of the screening failure rate in combination with the non response evaluable rate to account for participants who may drop out of the study without being evaluable for response and/or true recruitment rate is much higher than anticipated and thus, Sponsor will examine on the totality of data to determine the benefit/risk ratio as well as overall clinical activity when making the final Go/no Go decision.

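### The synopsis total of about 310 dosed subjects does not match the planned parts, which sum to about 430, and the Part C cohort size is given as both 25 and 40

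*Combined protocol and SAP*

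**What the plan says.** The only study-level total in the text available is in the synopsis, under Number of Subjects: "Approximately 310 subjects will be dosed".

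The part sizes are given as follows.

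- **Parts A and B.** Section 8.1.1: "Approximately 60 subjects are expected to be treated during the dose-escalation phase". This is split as about 30 on monotherapy and about 30 on the combination, and the synopsis agrees.
- **Part C.** The synopsis (Study Design) ends its description of the two populations with "and persistent, recurrent, or metastatic cervical cancer, of approximately 25 subjects each". Section 8.1.2 agrees: "Part C contains 2 cohorts of 25 subjects each in monotherapy cohort expansion". Section 3.1 describes the same two populations but ends with "and persistent, recurrent, or metastatic cervical cancer, of approximately 40 subjects each". Later in Section 3.1 the Part C arm is put at about 25. Section 3.5 gives about 40 for every expansion cohort without excepting Part C, and refers to Section 8.1.2 for details.
- **Part D.** Six tumour types; the synopsis list ends "v) ovarian cancer, and (vi) hepatocellular carcinoma of approximately 40 subjects each".
- **Parts D and E.** Section 8.1.2: "Each cohort in the combination cohort expansion phase (parts D and E) will contain approximately 40 subjects". Part E has two cohorts (9 and 10).

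The synopsis also qualifies the cohort sizes: "The planned sample size for each of the expansion cohorts serve as a guidance". Section 8.1.2 adds that they are approximate and may be exceeded.

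**The concern.** A study total should equal the sum of its parts to within rounding. Here the eight combination expansion cohorts by themselves exceed the total given for all five parts.

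The synopsis is where an ethics committee, a site or a safety reader looks for the number of people the plan would expose. For a first-in-human antibody, a headline figure well below what the design sections describe is a material inconsistency. It also clashes with the rationale for cohort size. Section 8.1.2 justifies 40 per combination cohort by a confidence-interval width goal and by response probabilities computed at 40, and a total of 310 cannot accommodate eight such cohorts.

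The Part C conflict is a second, smaller fault. It leaves the planned number on monotherapy expansion open between two values.

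**Working it through.** **Inputs**

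| Part | Planned size | Subtotal | Where stated |
|---|---|---|---|
| A and B | 30 + 30 | 60 | Synopsis; 3.4.1; 8.1.1 |
| C | 2 × 25 | 50 | Synopsis; 8.1.2 |
| D | 6 × 40 | 240 | Synopsis; 3.1; 8.1.2 |
| E | 2 × 40 | 80 | Synopsis; 3.1; 3.5; 8.1.2 |

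The Part C size cells in synopsis Table -2 and in Table 3.5-1 could not be read in the text available and were not used.

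**Sum.** 60 + 50 + 240 + 80 = 430.

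**Gap.** 430 − 310 = 120. As a share of the plan's sum, 120/430 = 27.9%. As a share of the stated figure, 120/310 = 38.7%.

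**Parts D and E alone.** 8 × 40 = 320, which is greater than 310.

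**Can 310 be reproduced?** Not from the current sizes.

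- Part C at 40 per cohort: 60 + 80 + 240 + 80 = 460, which is 150 above 310.
- Part C read as 25 in all (the literal sense of the later sentence in Section 3.1): 60 + 25 + 240 + 80 = 405.
- Leaving out Part E: 60 + 50 + 240 = 350. Leaving out Part C: 60 + 240 + 80 = 380. Expansion only: 50 + 240 + 80 = 370.
- Parts A, B and D only: 60 + 240 = 300. This is near 310 but drops two whole parts.
- Counting the Part E safety lead-in (6 to 12 subjects) as additional: 436 to 442, which widens the gap.

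Exactly 310 does arise from sizes the current plan does not use: 60 + 10 × 25 (all ten expansion cohorts at 25), or 60 + 50 + 5 × 40 (five Part D cohorts and no Part E). Either could be a remnant of another design, but the documents do not say so and the point does not depend on it.

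**What 310 would imply.** With escalation and Part C as planned, 310 − 60 − 50 = 200 subjects remain for eight combination cohorts. That is 200/8 = 25 each, against the 40 on which Section 8.1.2 bases its calculations.

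**Part C.** At 25 per cohort, 2 × 25 = 50. At 40 per cohort, 2 × 40 = 80. The difference is 30 subjects, and it plays no part in the 120 gap, which already uses the smaller value.

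**The case against.** The best defence is that this is one stale summary line with no inferential consequence. The same synopsis gives every component, so planned exposure is not hidden. The study tests no formal hypothesis, and the expansion toxicity trigger is a rate (33%) that does not depend on the total. All of this stands, and it limits the point to consistency and stated exposure.

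A second argument is flexibility. Cohort sizes are called guidance, the Part E cohorts are described as at most 40 (synopsis and Section 3.6.1), and Sections 3.7 and 8.1.2 allow enrolment decisions on accumulating data. On that view 430 is a full-enrolment sum and 310 an expectation. It is fair that 430 is a sum of targets rather than a proven intention. But nothing links 310 to an expected reduction. Where Section 8.1.2 gives a direction, it is upward, and replacing subjects who discontinue adds to the number dosed.

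Third, a breakdown with 60 for escalation is itself out of step with the safety update in Section 1.6. At 12 December 2016 that update counts 34 subjects on monotherapy and 50 on the combination, under a heading for Parts A and B. If all belong to escalation, that is 84, and 84 + 370 = 454. This is a reason to check the breakdown against subjects already treated. It moves the total further from 310, not closer.

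Fourth, the Part C conflict largely resolves in favour of 25, because Section 8.1.2 is explicit and Section 3.5 defers to it. That is a sound reading, but Sections 3.1 and 3.5 still contain text that contradicts it.

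**Conclusion.** The concern holds. The stated total of about 310 is 120 below the sum of the planned parts, about 430. Every reading of Part C gives between 405 and 460, so the conclusion does not depend on resolving that conflict. Neither the word approximately nor the guidance status of the cohort sizes covers a gap of 28%.

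The Part C size is also inconsistent, at 25 or 40 per cohort (50 or 80 in all). The better-supported value is 25.

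The sum assumes full enrolment at the stated cohort sizes, with the Part E lead-in counted within its 80 and no replacements. The documents do not establish which total the sponsor intended, only that 310 and the described parts cannot both be right. No estimate, interval or decision rule is affected.

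**What to change.** 1. In the synopsis, restate the total as approximately 430 and give the breakdown: Parts A and B 60, Part C 50, Part D 240, Part E 80. Check the escalation entry against the numbers already treated in Section 1.6. If 310 is the intended figure, state instead which cohorts are reduced and to what size, and revise the rationale in Section 8.1.2 for any combination cohort no longer planned at 40.
2. Use one Part C size in the synopsis, Sections 3.1, 3.5 and 8.1.2, and the two expansion-cohort tables: 25 per cohort if Section 8.1.2 governs. Make clear in Section 3.1 that the figure is per cohort.
3. In Section 3.5, limit the general statement of about 40 per cohort to Parts D and E.

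If 430 is confirmed, the cost is wording in the synopsis and Sections 3.1 and 3.5. The cohorts described in Section 8.1.2, and the calculations there, stay as they are.

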1 INTRODUCTION AND STUDY RATIONALE

Antibody-based therapy for cancer has become established in recent years and is now one of the most successful and important strategies for treating patients with hematological malignancies and solid tumors.¹ Aside from targeting antigens that are involved in cancer cell proliferation and survival, antibodies can also function to either activate or antagonize immunological pathways that are important in cancer immune surveillance. It is now clear that an antigen-specific anti-cancer immune response is the result of a complex dynamic interplay between antigen-presenting cells (APC), T lymphocyte (T) cells, and the target cancer cells.² The critical balance of T-cell activity that dictates whether endogenous anti-tumor immune responses will be effective, are largely understood to be controlled by antigen-specific stimuli sensed by the T-cell receptor and by the combined activity of both positive (co-stimulatory) and negative (co-inhibitory) T-cell surface molecules.³ Within the past decade, antibodies against these key receptors have been designed and evaluated in the clinic with impressive results, heralding the onset of immunotherapy as a key pillar of anticancer therapy.⁴

The most extensively studied immunotherapies in cancer are the negative regulatory receptors, cytotoxic T lymphocyte associated antigen 4 (CTLA-4), and programmed death-1 (PD-1).⁵ Inhibition of these negative regulatory receptors, referred to as immune checkpoint blockade, results in the enhanced activation of T-cell responses and potent antitumor activity in preclinical models. Trials with CTLA-4 blockade provided the first clinical evidence of improvement in overall survival with immune modulatory anticancer therapy in patients with metastatic melanoma.^{6,7} Following that, Topalian et al. showed that anti-PD-1 antibody produced objective responses in patients with non-small cell lung cancer (NSCLC), melanoma, and renal-cell cancer (RCC).⁸

Following on the success of CTLA-4 and anti-PD-1 pathway-targeted agents, the field of tumor immunotherapy is beginning to expand rapidly. In addition to blocking co-inhibitory pathways, activating co-stimulatory pathways to potentiate antitumor immune responses is being considered as a promising approach.⁹ Members of the tumor necrosis factor receptor superfamily (TNFRsf) include several co-stimulatory proteins with key roles in B and T cell development, survival, immune activation, and antitumor immune responses.¹⁰ Preclinical data have provided the basis for the trial of agonist antibodies to TNFRsf co-stimulatory receptors 4-1BB,^{11,12} OX40,^{13,14} glucocorticoid-induced TNFR-(GITR)-related gene,^{15,16} and CD27^{17,18} as potential therapies for patients with cancer. Overall, enhancement of the magnitude and potency of tumor antigen-specific adaptive cellular responses by CD8 and CD4 T cells is now considered a major goal in cancer immunotherapy.

With these recent emerging clinical lines of evidence of significant activity of single agent immunotherapies, it is possible that combination therapies could potentially lead to greater depth of response and overall survival as has been noted with the combination of anti-PD-1 and anti-CTLA4 in advanced melanoma patients.^{19,20} This raises the possibility that combining strategies

involving a broader range of immunotherapies, e.g. checkpoint blocking antibodies with antitumor immune pathways such as agonist antibodies to T-cell co-stimulatory molecules, could potentially lead to durable, long term responses and possibly even cures in this high unmet medical need population of patients with metastatic or refractory tumors. Pre-clinical data from evaluation of combinations in mouse tumor models indicate that treatment with the combination of both agents can lead to enhanced antitumor activity above that from each agent alone²¹ Patients with metastatic or refractory tumors have a very poor prognosis.²² Traditional or conventional treatment options for patients with advanced cancer include surgery, radiation, chemotherapy, hormone therapy, and immunotherapy, all of which have differing mechanisms of action. Despite advances in multimodal therapy, increases in overall survival in this patient population have been limited.

CA009002 is a Phase 1/2a, first-in-human (FIH), ascending multiple-dose study of BMS-986156, an anti-GITR agonistic antibody, in humans with advanced/metastatic solid tumors as monotherapy and in combination with nivolumab. This study will evaluate the safety profile, tolerability, preliminary efficacy, PK, [REDACTED] of intravenous (IV) doses of BMS-986156 administered every 2 weeks as monotherapy and in combination with nivolumab in advanced solid tumors and is expected to determine the maximum tolerated dose (MTD)/maximum administered dose (MAD) or an alternate dose(s) of BMS-986156 to be used in future monotherapy and combination with nivolumab therapy trials. In addition, the study will evaluate BMS-986156 as monotherapy and in combination with nivolumab in the following disease-restricted populations, as follows: NSCLC with progressive disease during, or recurrent disease, during or after anti-PD-1 or anti-programmed death-ligand (PD-L1), and persistent, recurrent, or metastatic cervical cancer. Additional tumor types are bladder cancer, head and neck squamous cell cancer, ovarian cancer, and hepatocellular carcinoma (HCC) (see [Section 3.9.1](#)).

Non-Small Cell Lung Cancer

Non-small cell lung cancer remains the leading cause of cancer-related mortality worldwide, accounting for approximately 18% of all cancer deaths.²³ Lung cancer is also the leading cause of cancer death in the US. In 2014, an estimated 224,210 new cases were expected to be diagnosed, and 159,260 deaths are estimated to occur because of the disease, accounting for 27% of all deaths due to cancer.²⁴

Most lung cancers (~ 80%) are NSCLC.²⁵ Of these patients, more than 65% present with locally advanced or metastatic disease.²⁶ Despite treatment with platinum-based chemotherapy, the standard of care for first-line therapy, patients with metastatic NSCLC have a median survival of approximately 10 months and a 5-year survival rate of less than 5%,²⁷ and treatment options for epidermal growth factor receptor (EGFR) and anaplastic lymphoma kinase (ALK) wild-type NSCLC are particularly limited after failure of front-line chemotherapy. Overall, this group of patients only has an OS of about 8 months after progression from platinum agents. Once resistance to tyrosine kinase inhibitors (TKIs) occurs, the patients who have EGFR mutations or ALK translocations often have a rapid disease progression.

Recently, nivolumab was approved for the management of advanced squamous and non-squamous NSCLC after there was demonstrable survival difference compared to chemotherapy.²⁸ However, the possibility that combining anti-PD-1 antibody with other agents could potentially lead to deeper and more durable long term responses in high PD-L1 expressing tumors and possibly even cures in this high unmet medical need population of patients with NSCLC provides additional rationale for evaluating novel combinations in this disease.

Carcinoma of the Cervix

Cervical cancer remains a considerable problem worldwide with 500,000 new cases and 250,000 deaths annually.²⁹ In 2014, in the US, an estimated 12,360 new cases were expected to be diagnosed, and 4,020 deaths are estimated to occur because of the disease.³⁰ Treatment for cervical cancer is typically surgery for Stages IA to IIA1 and concurrent chemoradiation for Stages IB2 to IVA. The 5-year survival rate for cervical cancer depends on stage and ranges from 93% for early stage disease (IA) to around 15% for Stages IVA and B.³¹ Treatment of recurrent disease is typically with surgery for resectable disease or chemotherapy plus bevacizumab, which improved objective response rate (ORR), (48% vs. 36%) and mOS (17 vs. 13.3 months) compared to chemotherapy alone.³² After first line chemotherapy, there is no standard of care that has demonstrated improved benefit over best supportive care.

Bladder Cancer

Bladder cancer is the ninth most common cancer in the world, with 430,000 newly diagnosed in 2012.³³ In the United States (US), approximately 77,000 new cases and 16,000 deaths occur each year due to bladder cancer.³⁴ In Europe, there were an estimated 118,000 cases and 52,000 deaths in 2012.³⁵ In developed regions such as North America and Europe, the histological phenotype is predominantly urothelial carcinoma.

From 1985 to 2005, the number of bladder cancers diagnosed in the US increased by more than 50%, while from 1975 to 1996, the five-year survival rate for those diagnosed with bladder cancer increased from 75% to 81%.³⁶ Mortality rates in several western European countries have shown similar downward trends over the last two decades but are still increasing in some eastern European countries.³⁶

Many bladder cancer patients do not die of their disease but do experience multiple recurrences. As a consequence, there are a relatively large number of people alive with a history of bladder cancer. In middle-aged and elderly men, bladder cancer is the second most prevalent malignancy after prostate cancer.³⁷

Squamous Cell Carcinoma Head and Neck

There are large geographic differences in the incidence and primary site of head and neck cancers. These likely reflect the prevalence of risk factors, such as tobacco and alcohol consumption, as well as ethnic and genetic differences among populations.

Although the highest rates of head and neck cancer are in older males, the incidence has been increasing in females as more women use tobacco, and in young non-smokers as human papillomavirus (HPV) plays an increasingly prominent role as an etiologic factor in the development of oropharyngeal head and neck cancer.

Tobacco (smoked and smokeless) is the most important known risk factor for the development of head and neck cancer. There is some evidence for a genetic predisposition to the carcinogenic effects of tobacco. In addition, tobacco and alcohol consumption appear to have a synergistic effect. The repeated exposure of the mucosa of the upper aerodigestive tract to the carcinogenic effects of tobacco, alcohol, or both appears to cause multiple primary and secondary tumors in this “condemned mucosa,” a phenomenon described as “field cancerization.”

HPV infection is a causative agent for head and neck cancer. HPV-associated head and neck cancers occur primarily in the oropharynx (tonsils and base of tongue), account for the younger age of patients with oropharyngeal squamous cell carcinoma, and define a subset of patients with improved treatment outcome. However, the use of HPV status in clinical decision making remains investigational at this time, and treatment is the same as for patients without an HPV-associated tumor.^{38,39,40,41,42,43,44}

Ovarian Cancer

The term ovarian cancer (OC) includes not only epithelial OC but also primary peritoneal and fallopian tube cancer. The latter two are less common neoplasms, which, however, are managed in a similar manner to epithelial OC. Epithelial OC is the leading cause of death from gynecologic cancer in the US and is the country’s fifth most common cause of cancer mortality in women. Nearly 75% of the patients present with advanced-stage OC.⁴⁵ According to the International Federation of Gynecology and Obstetrics, 5-year survival rates are approximately 46.7% for Stage IIIa, 41.5% for Stage IIIb, 32.5% for Stage IIIc, and 18.6% for Stage IV. Patients with platinum sensitive OC treated with platinum-based frontline therapy have high response rates of up to 81% and median progression free survival (mPFS) and mOS of 19.1 and 44.1 months, respectively.⁴⁶ However, patients with subsequent relapses, either platinum sensitive or resistant, have a significantly worse prognosis with mPFS between 10.2 and 4.1 months and mOS between 17.6 and 5.0 months, respectively,⁴⁷ Immunotherapy with weekly intraperitoneal IL 2 produced a ~17% complete pathologic response rate in patients with platinum-resistant OC.⁴⁸ A threefold prolongation of PFS was observed in patients treated with recombinant human IFN- γ combined with MTD cisplatin and cyclophosphamide chemotherapy, with minimal added toxicity.^{49,50} The presence of tumor-infiltrating lymphocytes (TILs) in advanced-stage OC correlates with an improved outcome. Patients with Stage III and IV OC and the presence of TILs within the tumor had better disease free survival and OS ($P < 0.001$) than did patients with similar staged OC and absence of TILs.⁵¹

Hepatocellular Carcinoma

Hepatocellular carcinoma is the fifth most common cancer worldwide and the second leading cause of cancer-related death. The incidence of HCC varies geographically largely due to variations in hepatitis B and C virus infection.

HCC has the highest mortality-to-incidence rate ratio of 0.98, followed by lung (0.85) and esophageal (0.83) cancers.⁵² The number of deaths is close to the number of new cases because most HCCs are detected at an advanced stage and occur in patients with underlying liver dysfunction, making HCC a highly lethal cancer. The prognosis is also poor because of the low effectiveness of available treatments. The 5-year HCC survival rate is approximately 5% to 6% compared with 72% and 22% for breast cancer stages III and IV, respectively.^{53,54,55} Treatment of HCC is challenging because the disease is highly heterogeneous with different etiologies and because of varying approaches to diagnosis and treatment and variations in responses to therapy.⁵⁶

Relatively few patients are eligible for curative treatment because of the late appearance of symptoms.⁵⁷ The majority of patients are diagnosed in the advanced stages of the disease when the disease is beyond resection and locoregional treatments are ineffective. The prognosis for these patients is poor.⁵⁸

GITR: Immune Activation by T cell Costimulation and Regulatory T cell Suppression

GITR protein (also known as TNFRsf18) was first identified as a dexamethasone-inducible molecule on a murine T cell hybridoma.⁵⁹ GITR is a type I transmembrane protein belonging to the TNFRSF including OX40, CD27, and CD137. These receptors are costimulators of T cell activity and with T cell receptor engagement result in T cell activation.

GITR is expressed on naive murine T cells but shows little expression on naive human T cells.⁶⁰ GITR is expressed upon activation of CD8 and CD4 effector T (Teff) cells, but is constitutively expressed on regulatory T (Treg) cells. In normal human peripheral blood mononuclear cells (PBMCs), GITR expression on Treg cells is higher than on conventional T cells, and while expression on resting CD4+ T cells was low it markedly increased after activation.⁶¹ It is also expressed on natural killer (NK) cells and at low levels on B cells, eosinophils, basophils, macrophages and dendritic cells, and can be upregulated by activation.^{62,63,64,65,66,67,68} GITR ligand is found largely on APCs.⁶⁹

GITR engagement on CD8 T cells has been shown to have an intrinsic effect of potentiating CD8 T cell activity.^{70,71} Additionally, GITR engagement has an intrinsic effect on CD8 T cell expansion.⁷² Consistent with its role in costimulation, GITR engagement promotes autoimmunity in autoimmune-prone mouse strains⁷³ similar to that observed upon blockade of the PD-1 pathway.⁷⁴ GITR signaling results in reduced T cell apoptosis and promotes T cell survival, at least in part by upregulating the expression of the Bcl-xL prosurvival molecule downstream of NFκB.⁷⁵

While Treg cells antagonize effector T cells, thereby limiting antitumor activity, engagement of GITR on Teff cells promotes increased T cell function by limiting the sensitivity of these cells to Treg suppression. Stephans et al mixed irradiated T-cell depleted splenocytes and anti-CD3, and Teff and Treg cells isolated from WT or GITR-deficient (GITR^{-/-}) mice, showing that GITR agonism renders Teff cells resistant to Treg suppression.⁷⁶ In addition, in certain circumstances engagement of GITR on intratumoral Treg cell may result in diminished suppressor activity. NK cells also express low levels of GITR, which can be up regulated by interleukin (IL)-2 and IL-15.⁷⁷ The consequences of GITR engagement on NK cells in antitumor responses remains to be determined because of conflicting data as to whether engagement increase⁷⁸ or decreases NK cell activity.⁷⁹

Rationale for BMS-986156 therapy

BMS-986156 is a fully human agonist antibody of the IgG1 isotype that binds with high affinity to the human GITR family related receptor. [REDACTED]

[figure not shown]

